5.1 Assignment of analysis sets

Final decisions regarding the assignment of subjects to analysis sets will be made during the review of study data and documented in the final list of important deviations, validity findings and assignment to analysis set(s) (see section [4.6](#)).

Safety analysis set

All subjects who received at least 1 dose of BAY 1163877 will be included in the safety evaluation.

MTD analysis set

All subjects who completed Cycle 1 or discontinued during Cycle 1 due to an adverse event or DLT in the dose escalation part will be included in the MTD evaluation.

Efficacy analysis set

All subjects who received at least 1 dose of BAY 1163877 and who have post-baseline efficacy data available will be included in the efficacy evaluations.

Pharmacodynamic analysis set

All subjects with evaluable PD data and who complete the study without major changes versus protocol will be included in the evaluation of PD.

Pharmacokinetic analysis set

All subjects with valid pharmacokinetic data will be included in the evaluation of pharmacokinetic concentrations and parameters.

6. Statistical Methodology

The treatment groups to be analyzed are defined in section [4.1](#).

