 - the MTD has been defined with good precision (i.e. the coefficient of variation for the MTD is lower than or close to 40%)
or
 - at any time when the selected dose level for the next cohort has already been given in 9 subjects.

If the dose escalation stops, the sample size for the MTD cohort will be expanded up to a total of 20 evaluable subjects (study Part 1 / MTD expansion cohort (all comer)).

No intra-subject dose escalation is permitted. Dose interruptions and / or dose reductions may be required based on individual safety and tolerability.

Variables are specified in the Clinical Study Protocol [\(2\)](#).

4. General Statistical Considerations

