4.2 Handling of Dropouts

A subject who discontinues study participation prematurely for any reason is defined as a “dropout” if the subject has already been administered at least 1 dose of the study drug (BAY 1163877).

A subject who, for any reason (e.g. failure to satisfy the selection criteria), terminates the study before the time point used for the definition of “dropout” (see above) is regarded a “screening failure”.

Subjects who discontinue due to a DLT will NOT be replaced.

Subjects who discontinue during the first cycle of therapy (Cycle 1) due to any reason other than a DLT and / or related toxicity, and subjects who took less than 80% of the required study drug (BAY 1163877) in Cycle 1 will be replaced to ensure 3 evaluable subjects per cohort for the determination of MTD and PK of BAY 1163877. Subjects who discontinue after the first cycle (Cycle 1) will not be replaced.

Subjects enrolled in Study Part 1 / MTD expansion (all comer) with insufficient paired biopsy samples will be replaced to ensure at least 10 subjects with paired biopsy samples for p-ERK1/2 analysis.

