5.1 Assignment of analysis sets

Final decisions regarding the assignment of subjects to analysis sets will be made during the review of study data and documented in the final list of important deviations, validity findings and assignment to analysis set(s) (see section [4.6](#)).

Safety analysis set

All subjects who received at least 1 dose of BAY 1163877 will be included in the safety evaluation.

MTD analysis set

All subjects who completed Cycle 1 or discontinued during Cycle 1 due to an adverse event or DLT will be included in the MTD evaluation.

Efficacy analysis set

All subjects who received at least 1 dose of BAY 1163877 and who have post-baseline efficacy data available will be included in the efficacy evaluations.

Pharmacodynamic analysis set

All subjects with evaluable PD data and who complete the study without major changes versus protocol will be included in the evaluation of PD.

Pharmacokinetic analysis set

All subjects with valid pharmacokinetic data will be included in the evaluation of pharmacokinetic concentrations and parameters.

6. Statistical Methodology

The treatment groups to be analyzed are defined in section 4.1. The tables, listings, and figures will be separately displayed for the different parts of the study (i.e. Part 1 dose escalation, Part 1 MTD expansion cohort “all comer”, Part 2 MTD expansion cohort “sqNSCLC + LAC+ BC + SCCHN”, and Part 3 MTD expansion cohort “Safety cohort”).

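### Sections 4.2 and 5.1 of the SAP disagree on who counts for the MTD, and the 5.1 set can dilute or lose dose-limiting toxicities

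*SAP*

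**What the plan says.** For the MTD evaluation, section 5.1 of the current SAP text (the supplement approved in December 2019) admits "All subjects who completed Cycle 1 or discontinued during Cycle 1 due to an adverse event or DLT in the dose escalation part". SAP Version 1.0 has the same criteria without the restriction to dose escalation: "All subjects who completed Cycle 1 or discontinued during Cycle 1 due to an adverse event or DLT will be included in the MTD evaluation".

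Section 4.2 governs replacement and has three parts:
- **Exposure:** "subjects who took less than 80% of the required study drug (BAY 1163877) in Cycle 1 will be replaced".
- **Reason for leaving:** replacement also applies to "Subjects who discontinue during the first cycle of therapy (Cycle 1) due to any reason other than a DLT and / or related toxicity".
- **Protection:** "Subjects who discontinue due to a DLT will NOT be replaced".

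Section 4.2 gives the purpose of replacement as "to ensure 3 evaluable subjects per cohort for the determination of MTD and PK of BAY 1163877", so the rule is about the MTD and not only about PK. Reduced exposure is foreseen: at the end of section 3 the SAP states "Dose interruptions and / or dose reductions may be required based on individual safety and tolerability".

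Section 6.4.2 summarises Cycle 1 DLT incidence and models it by Bayesian logistic regression. Neither 6.4.2 nor 6.5 names the MTD analysis set, and the opening of section 6.4 assigns its analyses to the safety set.

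**The concern.** The two sections apply different tests to the same subjects. Section 4.2 tests exposure and whether the toxicity was related. Section 5.1 tests only completion, or discontinuation for any adverse event or DLT. A subject can therefore be judged inadequate for the MTD and replaced, and still stay in the MTD denominator beside the replacement. In the other direction, 5.1 decides inclusion by the reason for stopping and not by whether a DLT occurred, so a DLT can drop out of the numerator.

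Determining the MTD is a primary objective, with a limit of 20% of subjects with a DLT in Cycle 1. Cohorts have 3 or 4 subjects and a dose level has at most 9, so one or two subjects are enough to change the estimate visibly.

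**Working it through.** **1. The two rules side by side**

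| Subject in dose escalation | Section 4.2 | Section 5.1 MTD set |
|---|---|---|
| A. Completes Cycle 1, under 80% of drug, no DLT | replaced | included |
| B. Leaves Cycle 1 for an unrelated adverse event, no DLT | replaced | included |
| C. Has a DLT, but the recorded reason for leaving Cycle 1 is progression or withdrawal | replaced, on a literal reading | not included |
| D. Has a DLT, stays on, completes Cycle 1 on under 80% of drug | replaced, on a literal reading | included |
| E. Leaves Cycle 1 for related toxicity that is not a DLT | not replaced by the discontinuation part; replaced by the 80% part if intake was under 80% | included |
| F. Leaves Cycle 1 for progression or withdrawal, no DLT | replaced | not included |

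A and B add DLT-free subjects to the denominator. C removes a DLT. D and E show that 4.2 is itself incomplete. F is handled consistently.

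**2. Direction**

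Take as reference all subjects with a Cycle 1 DLT plus adequately dosed DLT-free subjects, with r DLTs among n.
- Adding k subjects of type A or B gives r/(n+k), which is at most r/n and equals it when r = 0.
- Losing one subject of type C gives (r−1)/(n−1), which is below r/n whenever r < n.

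Neither route can raise the crude rate.

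**3. Size in crude rates (hypothetical counts)**

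The SAP does not say how many such subjects there are, so I assume one or two at a dose.
- 1/3 = 33.3%; one added: 1/4 = 25.0%; two added: 1/5 = 20.0%.
- 2/6 = 33.3%; one added: 2/7 = 28.6%; two added: 2/8 = 25.0%.
- 2/6 with one DLT subject lost: 1/5 = 20.0%.

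For expected rates, let p be the full-dose DLT rate, u the share of under-dosed subjects and f their relative DLT risk. The rate in the set is (1−u)p + u·p·f. With p = 25% and u from 10% to 30%, it is 22.5% to 17.5% if f = 0, and 23.8% to 21.2% if f = 0.5. If a share w of DLT subjects is lost, the rate is p(1−w)/(1−pw). With p = 25% and w from 10% to 30%, it is 23.1% to 18.9%.

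**4. Size in the SAP's own model**

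Inputs from section 6.5: logit(p) = intercept + slope × dose; intercept normal with mean −3 and variance 1; slope positive normal with mean 0.0015 and variance 0.003; MTD = (log(0.2/0.8) − intercept)/slope. Dose levels from section 4.1: 100, 200, 400, 800, 1200 and 1600 mg/day. Assumptions: dose enters as mg per day, and there are 0/3 DLTs at each of the five lower doses. The posterior was computed on a grid.

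| Data at 1600 mg/day | Median MTD (mg/day) | Posterior mean DLT rate at 1600 | P(p < 0.20) at 1600 |
|---|---|---|---|
| 2/6 (reference) | 1479 | 25.5% | 42% |
| 2/7 (one type A or B added) | 1583 | 22.7% | 49% |
| 2/8 (two added) | 1684 | 20.5% | 55% |
| 1/5 (one type C lost from 2/6) | about 2050 | 16.6% | 69% |

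Going from 2/6 to 2/8, the median MTD crosses 1600 mg/day.

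**The case against.** **The effect depends on the example chosen.** This stands. A reader might infer from 2/9 = 22.2% against 2/11 = 18.2% that the set definition flips a dose from above to below the limit. In the model that computes the MTD, it does not: the posterior mean at 1600 mg/day is already 18.8% with 2/9 and falls to 16.1% with 2/11. The median MTD is above 1600 in both cases (1782 and 1974). Only the crude rate crosses 20%. The 2/6 to 2/8 example does cross 1600 in the model, so the effect is real but not universal.

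**Escalation decisions did not rest on this set.** Largely true. Sections 3 and 4.4 give the decision to the sponsor and investigators on all available data, and section 6.5 does not say that the interim model used the 5.1 set. Section 4.1 of the supplement already lists the expansion groups at 800 mg BID. What the set plausibly governs is the reported DLT incidence and the final posterior.

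**Section 4.2 is a replacement rule and never says that replaced subjects leave the analysis.** Correct as to wording. But replacing subjects to obtain evaluable ones for the MTD has little point if the replaced subjects are evaluable too.

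**Data review settles assignment.** Section 5.1 does defer final assignment to the review of study data, but it gives no exposure or DLT criterion. In an open-label trial that choice would be made with the DLTs known.

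**The protocol may define evaluability.** It may. The SAP still contradicts itself, and its supplement changed this definition only by restricting it to dose escalation.

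**Conclusion.** The inconsistency is real and should be fixed, though it does not have to block the analysis. Followed literally, 5.1 keeps DLT-free subjects whom 4.2 replaces and can omit a subject with a DLT. Against the reference set in the check, the crude DLT rate can only fall or stay the same. The illustrated size is a shift in median MTD from about 1479 to 1684 mg/day and in P(p < 0.20) at 1600 mg/day from 42% to 55%. It rests on two added subjects, 0/3 at each lower dose, and dose in mg per day. The actual size is unknown and may be zero; a dose with no DLTs keeps a crude rate of zero.

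Three stronger readings are not supported:
- A reader might infer that all replaced subjects are counted as DLT-free. Those who left for progression or withdrawal without a DLT are already outside the set.
- A reader might infer that a subject whose DLT led to interruption and intake under 80% is lost. If that subject completes Cycle 1, 5.1 keeps the DLT; the fault is a missing exception in 4.2, not a bias in the set.
- A reader might infer that DLTs are lost routinely. Subjects with a DLT who complete Cycle 1, or who stop for the DLT or another adverse event, are all included. The lost case is narrow.

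Nothing in the SAP shows that the dose carried into expansion was affected.

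**What to change.** In section 5.1, define the MTD analysis set as dose-escalation subjects who meet one of these conditions:
- (a) had a DLT in Cycle 1, whatever the amount of drug taken or the reason for leaving;
- (b) completed Cycle 1 without a DLT on at least 80% of the required drug;
- (c) left Cycle 1 for drug-related toxicity that was not a DLT.

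Group (c) is needed because the discontinuation part of 4.2 does not replace these subjects. A set made only of (a) and (b) would leave them neither replaced nor evaluable, and a cohort could fall short of the three evaluable subjects that 4.2 intends. Exclude the other DLT-free subjects whom 4.2 replaces from numerator and denominator alike.

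Reconcile section 4.2 so that its 80% part never classes a subject with a DLT as non-evaluable, and so that its two parts agree on group (c).

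Name this set in 6.4.2 and 6.5, which also removes the ambiguity created by the safety-set sentence opening 6.4. Report two sensitivity analyses: the current 5.1 definition, and the new set without group (c).

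The cost is SAP wording, one re-derived population flag, and possibly a few subjects fewer in the denominator.

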4.1 General Principles

The statistical evaluation will be performed by using the software package SAS release 9.2 or higher (SAS Institute Inc., Cary, NC, USA), R release 2.4.1 or higher and BRugs release 0.3-3 or higher. All variables will be analyzed by descriptive statistical methods. The number of data available, mean, standard deviation, minimum, median, and maximum will be calculated for metric data. Frequency tables will be generated for categorical data.

Data displays will follow the standard table catalogs for oncology standards, global standards, and clinical pharmacology standards, respectively.

The pharmacokinetic parameters will be evaluated statistically in accordance with pertinent company guidelines.

The following treatment groups will be analyzed:

- Total Dose Escalation – It contains all cohorts from the escalation phase:
 - 100 mg BAY 1163877 (50 mg solution BID)
 - 200 mg BAY 1163877 (100 mg solution BID)
 - 400 mg BAY 1163877 (200 mg tablet BID)
 - 800 mg BAY 1163877 (400 mg tablet BID)
 - 1200 mg BAY 1163877 (600 mg tablet BID)
 - 1600 mg BAY 1163877 (800 mg tablet BID)
- Expansion All Comers – Expansion phase, 1600 mg BAY 1163877 (800 mg tablet BID), cancer type does not fit the categories below
- Expansion Bladder – Expansion phase, 1600 mg BAY 1163877 (800 mg tablet BID), cancer type: bladder cancer

Statistical Analysis Plan

Protocol No.: **BAY 1163877/16443**

Page: 11 of 20:

- Expansion Head & Neck – Expansion phase, 1600 mg BAY 1163877 (800 mg tablet BID), cancer type: squamous carcinoma cell head and neck
- Expansion NSCLC – Expansion Phase, 1600 mg BAY 1163877 (800 mg tablet BID), cancer type: lung adenocarcinoma / squamous cell carcinoma

The categories of region used for subgroup analysis will be derived for each subject by using the variable country (location of the respective site).

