6.2 Efficacy

Efficacy analyses will be performed on the efficacy analysis set.

Tumor response

Efficacy data, such as best tumor response, will be summarized using descriptive statistics and will be graphically displayed if appropriate. The correlation between PD parameters and selected safety, efficacy, or PK parameters may be graphically displayed. Further statistical analyses may be conducted.

The efficacy analysis will include descriptive analyses on response rate, progression-free survival (PFS), time to progression (TTP), duration of response (DOR), and duration of treatment (DOT).

Response as defined by RECIST v.1.1: complete response (CR), partial response (PR), stable disease (SD), progressive disease (PD). Response and progression will be evaluated in this trial using the new international criteria proposed by the RECIST committee for solid tumor.

PFS is defined as the time (days) from the date of the first dose of study drug to the date of the first observed disease progression (radiological or clinical) or death due to any cause, if death occurs before progression is documented. PFS for subjects without tumor progression at the time of analysis will be censored at their last date of tumor evaluation.

TTP is defined as the time from start of study treatment until first observed disease progression (radiological or clinical). In comparison to PFS, TTP does not consider death as an event.

DOR (for partial and complete response (PR/CR)) is defined as the time (days) from the first documented objective response of PR or CR, whichever is noted earlier, to disease progression or death (if death occurs before progression is documented).

Kaplan-Meier (KM) product-limit estimates for median, 25th and 75th percentile with its 95% CI together with total number of subjects, total censored and total events will be provided for PFS and TTP per treatment. In addition KM survival curves will be presented for each treatment group.

Best overall tumor response according to RECIST criteria will be summarized by treatment group and region (Asia, ROW, and total) using frequency counts.

Best % Change in Target Lesion sum of diameter from Baseline will be displayed graphically for all subjects from worst to best in a waterfall plot.

Subgroup analysis will be performed by prior immunotherapy information (prior immunotherapy vs. no prior immunotherapy) .

Statistical Analysis Plan

Protocol No.: BAY 1163877/16443

Page: 15 of 20:

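### The efficacy set drops treated subjects with no post-baseline efficacy data from the response-rate denominator; whether PFS is also affected turns on an undefined term, and duration of response has no censoring rule or Kaplan-Meier estimate

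*SAP*

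**What the plan says.** The current text is the SAP supplement approved on 11 December 2019. Its section 5.1 fixes who enters the efficacy analysis set: those who took at least one dose "and who have post-baseline efficacy data available will be included in the efficacy evaluations". Version 1.0 has the same definition. Section 6.2 of the supplement adds: "Efficacy analyses will be performed on the efficacy analysis set". No other set is named for efficacy.

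Section 6.2 lists the variables: "The efficacy analysis will include descriptive analyses on response rate, progression-free survival (PFS), time to progression (TTP), duration of response (DOR), and duration of treatment". The response categories are CR, PR, SD and PD, with no category for subjects not assessed or not evaluable. PFS runs from first dose "to the date of the first observed disease progression (radiological or clinical) or death due to any cause, if death occurs before progression is documented". Subjects without progression are censored at their last tumour evaluation, and no rule covers a subject who has no evaluation after baseline.

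Duration of response runs from the first PR or CR to progression or death. No censoring rule is given for it. Kaplan-Meier median and quartiles, with "total censored and total events will be provided for PFS and TTP per treatment", do not extend to it. The general rule in section 4.1 is: "The number of data available, mean, standard deviation, minimum, median, and maximum will be calculated for metric data".

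Section 4.3 says that missing data are not replaced. Section 6.1 foresees that the efficacy and safety populations may differ, but repeats only the population-characteristics summaries in that case.

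**The concern.** Membership of the efficacy set depends on something that happens after treatment starts. A treated subject who stops for toxicity, deteriorates or withdraws before any assessment is lost from the denominator, and such subjects are by construction not documented responders. The error in the response rate therefore has one direction.

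For PFS the difficulty is that post-baseline efficacy data is not defined. The SAP does not say whether a subject who dies or progresses clinically before the first scan belongs to the set. Section 5.1 leaves final assignment to the review of study data, and the trial is open-label, so the question would be settled with outcomes in view.

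For duration of response, a responder who leaves without progression has an incomplete duration. Section 3 ends follow-up 30–35 days after the last dose and plans no long-term follow-up. A plain mean or median treats an incomplete duration as complete, or drops it.

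Part 2 is meant to look for preliminary clinical responses, and Part 3 collects further efficacy data. No efficacy test is planned, so the estimates are themselves the result, and their denominator and estimator matter.

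**Working it through.** The SAP gives no expected response rate, median PFS, median duration of response, or share of subjects without post-baseline data, so it has no figure to reproduce. The values below are assumptions chosen to show size. Only the planned group sizes come from the SAP (section 3), and they are taken here as the numbers treated.

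**Response rate.** Let R be the responders, N the treated subjects and m the share without post-baseline data. All R responders remain in the set, so the reported rate is R/(N(1−m)), which is the all-treated rate divided by (1−m).
- Assumed rate 20%: 0.20/0.90 = 22.2% at m = 10%; 0.20/0.80 = 25.0% at m = 20%.
- SCCHN, at least 8 planned, assumed 2 responders: 2/8 = 25.0%; with one subject left out, 2/7 = 28.6%.
- NSCLC in Part 2, 20 planned, assumed 5 responders: 5/20 = 25.0%; 5/18 = 27.8% at m = 10%; 5/16 = 31.25% at m = 20%.
- BC at its maximum of 50, assumed 12 responders: 12/50 = 24.0%; 12/45 = 26.7% at m = 10%; 12/40 = 30.0% at m = 20%.

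**PFS.** Assume exponential times with a true median of 3 months and a first scan at about 6 weeks (1.38 months).
- Reading A: early deaths and clinical progressions do not count as efficacy data, and a share m of treated subjects, all with events before the scan, is left out. The median t of those remaining satisfies S(t) = 0.5(1−m), so t = 3 × [1 + log2(1/(1−m))].
  - m = 5%: 3 × 1.074 = 3.22 months
  - m = 10%: 3 × 1.152 = 3.46 months
  - m = 20%: 3 × 1.322 = 3.97 months
- Reading B: such events count. Those left out then have neither event nor scan. If kept, they would be censored at the start and would never be at risk when an event occurs, so the Kaplan-Meier curve is the same with or without them. The shift is nil.

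**Duration of response.** Assume exponential times with a true median of 6 months (rate λ = ln 2/6 = 0.1155 per month) and censoring uniform on 0 to F months. The censored share is (1−e^(−λF))/(λF). The plain median of the recorded durations solves e^(−λt)(1−t/F) = 0.5.
- F = 36: (1−0.0156)/4.159 = 24% censored; plain median about 4.8 months.
- F = 12: (1−0.25)/1.386 = 54% censored; plain median about 3.3 months.
- Simulation of 200,000 durations with F = 12: plain median 3.26 months, median among progressed responders only 2.55, Kaplan-Meier median 5.99.

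**The case against.** The strongest reply concerns PFS. A reader might infer that the SAP removes early deaths and clinical progressions and so certainly inflates PFS. It does not say that. Section 5.1 speaks of efficacy data, not of scans, and section 6.2 makes death and clinical progression PFS events, so they can naturally be read as efficacy data. On that reading there is no bias. This stands: the defect is an undefined term, not a stated exclusion. A larger shift, to 3 + 1.38 = 4.4 months, could be obtained by dropping every event before the assumed scan (1 − 0.5^(1.38/3) = 27% of subjects). That is a worst case which nothing in the SAP supports.

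A reader might also infer that the SAP prescribes a biased summary of duration of response. It does not. It promises a descriptive analysis and omits the method. The sentence on Kaplan-Meier curves by treatment group names no endpoint and so does not rule this variable out. Heavy censoring is not established either, since treatment continues until progression or while benefit is assumed, in a study of about 7 years. The point is an omission, harmful only if the section 4.1 default is applied to censored responders.

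Finally, tumour response is a secondary objective, no test or threshold is attached to it, and the search for clinical responses is stated for Part 2 only. Set assignments are documented, disposition covers all subjects assigned to treatment, and deaths are listed, so an all-treated rate could be recomputed. This lowers the consequence. It does not answer the response-rate point, because the rate planned for reporting would still be the inflated one.

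**Conclusion.** The response-rate point holds on the plain wording: its direction is certain, and its size is the factor 1/(1−m). The value of m is not in the SAP; at an assumed 10–20%, a 20% rate is reported as 22–25%, and in a group as small as SCCHN a single subject matters.

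The PFS point holds conditionally. The shift lies between nil and, for an assumed 3-month median with 5–20% left out, about 0.2 to 1.0 month, depending on how an undefined term is read.

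The duration-of-response point holds as a gap in specification. Filling it with the general summary could turn an assumed 6-month median into about 4.8 or 3.3 months under the censoring patterns shown.

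None of this touches an error rate or a sample size. It should be corrected because the descriptive estimates are the efficacy result.

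**What to change.** - **Response rate:** use all treated subjects (the safety analysis set) as the denominator. Count subjects without a post-baseline tumour assessment as non-responders and show them as a separate category in the best-response table.
- **PFS and TTP:** use the same set. Early death or clinical progression is a PFS event, and clinical progression is a TTP event. Censor at Day 1 when there is neither an event nor a post-baseline assessment.
- **Present efficacy set:** keep it as a sensitivity analysis and define post-baseline efficacy data explicitly, stating whether death and clinical progression qualify.
- **Duration of response:** apply the PFS censoring rule and add the variable to the Kaplan-Meier estimates.

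The cost is SAP wording, one extra denominator and one extra Kaplan-Meier table. The reported response rate will be slightly less favourable. No new data are needed.

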Subjects will continue receiving treatment until tumor progression, unacceptable toxicity, consent withdrawal, or subject withdrawal from the study at the discretion of the Investigator or his/her designated associate(s). As long as, in the judgment of the subject and the investigator, some benefit with evidence of tumor reduction or stable disease is being derived, dosing with BAY 1163877 may continue.

Determination of the MTD

An adaptive dose escalation design will be used to determine the MTD in study Part 1 / dose escalation (all comer). The MTD is defined as the highest dose that can be given such that not more than 20% of subjects experience a DLT during Cycle 1.

Without the occurrence of toxicities, dose escalation could be stopped and RP2D may be determined based on PK and/or PD results. The decision to continue treatment for an individual subjects will be made by the investigator according to the criteria specified in the protocol.

Each cohort will be evaluated after all subjects have completed the first 21 days of treatment (which will subsequently referred to as “Cycle 1”) or early discontinued.

Statistical Analysis Plan

Protocol No.: **BAY 1163877/16443**

Page: 9 of 20:

Safety monitoring will occur by telephone conferences with participation of the investigators and the sponsor on a regular basis.

At the time of dose escalation the available clinical safety information is discussed in a telephone conference by the involved investigators and representatives from the Sponsor including the Study Medical Expert as well as representatives of other clinical and if required further contributing functions (drug safety monitoring team – DSMT). During this telephone conference it will be judged if dose escalation can proceed as planned according to the procedure outlined below. Dose escalation for subsequent cohorts will only be considered after full evaluation of at least Cycle 1 safety data from the previous cohort.

The National Cancer Institute (NCI) Common Terminology Criteria for Adverse Events Version 4.03 (CTCAE v4.03) will be used to grade toxicities / adverse events.

The dose escalation will be performed as follows:

- Initially 3 subjects per dose level will be enrolled. In case 2 or more sites are conducting the dose escalation part, the initial enrolment of 4 subjects per dose level is optional.

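### The pharmacodynamic analysis set (SAP section 5.1) requires study completion, an undefined condition that can exclude subjects with evaluable PD data

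*SAP*

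**What the plan says.** SAP section 5.1 sets two joint conditions for the PD set: "All subjects with evaluable PD data and who complete the study without major changes versus protocol". The wording is the same in SAP Version 1.0 and in the later supplement.

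Section 3 gives treatment no fixed end: "Subjects will continue receiving treatment until tumor progression, unacceptable toxicity, consent withdrawal", or withdrawal at the investigator's discretion. It also says that a subject who starts new anti-cancer therapy is no longer on study, and it places the follow-up visit 30 to 35 days after the last dose.

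Section 4.2 contains the nearest thing to a definition of a non-completer: "A subject who discontinues study participation prematurely for any reason is defined as a" dropout, provided that at least one dose was given. The same section says that subjects in the Part 1 all-comer expansion "with insufficient paired biopsy samples will be replaced to ensure at least 10 subjects with paired biopsy samples for p-ERK1/2 analysis", and that "Subjects who discontinue after the first cycle (Cycle 1) will not be replaced".

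Evaluating PD parameters is a secondary objective (section 2).

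**The concern.** A PD measurement with a valid baseline and a valid on-treatment value does not become invalid because the subject later withdraws, dies or changes therapy. A completion condition therefore removes usable data because of an event after dosing. Such events may be related to toxicity or progression, so the subjects who remain may differ systematically from those who supplied PD data. Section 6.2 allows PD parameters to be plotted against safety, efficacy or PK parameters, and a selection of this kind could distort those displays.

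The rule also sits badly with section 4.2. Effort is spent on obtaining at least 10 biopsy pairs, but a subject with a good pair who later fails the completion condition triggers no replacement.

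**Working it through.** The figure of at least 10 pairs is a target with no alpha, power, effect size or standard deviation behind it, so there is no calculation to reproduce. The check is a comparison of passages, followed by an illustration.

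**Conditions for the analysis sets (section 5.1)**

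| Set | Condition | Study completion required? |
|---|---|---|
| Safety | at least 1 dose | No |
| Efficacy | at least 1 dose and post-baseline efficacy data | No |
| PK | valid PK data | No |
| MTD | Cycle 1 completed, or Cycle 1 discontinuation for an adverse event or DLT | No, Cycle 1 only |
| PD | evaluable PD data and study completion without major protocol changes | Yes |

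Only the PD set looks beyond the data to the end of the study, and no reason is given.

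**What completion could mean**

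1. *Lenient reading.* Progression or toxicity is an expected end of treatment, and a subject who then attends the end-of-treatment and follow-up visits has completed. Only withdrawal, death or loss before follow-up excludes a subject.
2. *Strict reading.* Every dropout under section 4.2, or every subject who starts new therapy before the follow-up visit and so is no longer on study, is a non-completer. More subjects are excluded.

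The SAP does not choose between these readings.

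**Replacement against inclusion**

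- The biopsy replacement rule in section 4.2 depends on insufficient pairs. A subject with a sufficient pair is not replaced under it, whatever happens later.
- The other replacement rule (Cycle 1 discontinuation for reasons other than a DLT or related toxicity, or less than 80% of study drug taken) serves MTD and PK evaluability.
- Discontinuation after Cycle 1 is not replaced.

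So if p-ERK1/2 is evaluated on the PD set, the number of pairs collected and the number analysed can differ.

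**Illustration only**

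The completion probability c is an assumption, because the SAP gives none. Take exactly 10 pairs and independent subjects. Expected pairs kept = 10c, and the probability of keeping all 10 = c^10.

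| c (assumed) | Expected pairs kept | Probability that all 10 are kept |
|---|---|---|
| 0.9 | 9 | 0.9^10 = 0.35 |
| 0.8 | 8 | 0.8^10 = 0.11 |
| 0.7 | 7 | 0.7^10 = 0.028 |
| 0.5 | 5 | 0.5^10 = 0.001 |

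The starting point of 10 is the minimum. The all-comer MTD cohort is planned at 20 evaluable subjects. If all 20 supplied a pair, 20 × 0.5 = 10 would be expected to remain even at c = 0.5. The table shows that collecting 10 does not secure 10. It does not predict the loss.

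**The case against.** The strongest reply is that the rule may do little. On the lenient reading, subjects who progress and attend their last visits stay in the set. Section 4.2 is not linked to the PD set, and section 3 says that a subject on new therapy is no longer on study, not that the subject failed to complete it. Set assignment is decided and documented at the data review (sections 4.6 and 5.1). The supplement's section 6.1 adds summaries of the PD population where it differs from the safety population, so exclusions would be visible. Section 6.3.2 describes only cardiovascular parameters, and no section ties p-ERK1/2 to the PD set by name. That link is inferred from the set being the one used to evaluate PD.

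All of this stands as a limit on the size of the problem. It does not remove the wording. Even the lenient reading excludes subjects with valid data who withdraw or die, and leaving an undefined criterion to a data review in an open-label study means interpreting it after the data can be seen.

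Two stronger inferences are tempting.

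- A reader might infer that the set favours subjects who tolerated treatment and did not progress early. That needs the strict reading, which the SAP does not state.
- A reader might infer that 30% non-completion cuts 10 pairs to 7 and widens a 90% confidence interval for the mean change by 27% (1.943/√7 = 0.734 against 1.833/√10 = 0.580; ratio 1.27). The arithmetic is right, but the 30% is assumed, 10 is the minimum, and the SAP plans no confidence interval for p-ERK1/2. Its 90% intervals are for PK ratios and the DLT model.

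**Conclusion.** The point holds as a defect in the definition of one analysis set. The PD set carries an undefined completion condition that suits neither open-ended treatment nor the neighbouring sets, and as written it excludes some subjects whose PD data are evaluable. The consequence for the biopsy pairs is conditional on p-ERK1/2 being evaluated on this set. Section 4.2 governs how many pairs are obtained and does not promise a number analysed.

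The size ranges from small to material according to how completion is read. The documents do not allow a figure for the loss or a direction for any bias. The analysis is descriptive and secondary, so no primary conclusion is affected. The correction is still worth making because it settles the set before the data review and costs almost nothing.

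**What to change.** In section 5.1, delete the words *complete the study* and define the PD set as all treated subjects with a valid baseline and at least one valid post-dose value for the PD variable concerned. For biopsies, require an evaluable pair. Exclude only protocol deviations that affect that measurement, so that a subject may be in the set for one PD variable and not for another.

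The cost is one sentence in the SAP. No new data, visits or subjects are needed, and pairs obtained under section 4.2 would then be analysed unless such a deviation applied to them.
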